## General Information

RADx-UP is an ongoing research study funded by the National Institutes of Health to address COVID-19 testing disparities in vulnerable populations. The goal of RADx-UP is to reduce the burden of disease in vulnerable populations known to be at increased risk of severe COVID-19 infection (e.g., those with medical comorbidities, homeless, racial/ethnic minorities who live in rural communities). The focus of the Phase I main RADx-UP study was to examine COVID-19 testing to reduce infection transmission and prevalence. There are three sites (Houston, Northeast Texas, and South Texas). The Phase I main study questions were answered (approved under another IRB protocol) in a Randomized Control Trial (RCT) where 120 priority block groups were randomized to one of three conditions: 1) Multi-Level Intervention (MLI) group; 2) Community JITAI (Just-In-Time Adaptive Intervention) 3) Control group. The outcomes of this study were measured at the population level, and no individual data was gathered.

In Phase II, the embedded study was built off this main trial with some adjustments to the design because of expanded research priorities to include factors influencing antigen testing. The intervention priority census block groups (PBGs) that received either form of intervention in the main trial were combined into one pool of intervention PBGs for the embedded study. The control PBGs from the main trial remained the pool of control PBGs for the embedded study. A sample of intervention PBGs were randomly selected from across the three study regions and assigned to one of two intervention study arms. A sample of the control PBGs was randomly selected from across the three study regions and assigned to the control condition. We are recruiting and enrolling individuals from the selected PBGs across the three arms using systematic sampling with a random start.

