In Phases I and II, the PBGs were selected from the Harris/South Texas/NE Texas region at the ratio of 2:1:1, that is, 20 PBGs of MC-JITAI arm in Harris, 10 in South Texas, and 10 in NE Texas. Among the 40 PBGs in the control arm, all remain in the control group. During Phase II recruitment, we identified PBGs where recruitment was not feasible due to various factors (ex., dangerous areas, largely gated

neighborhoods, neighborhoods with HOAs that did not permit us entry into the neighborhood, etc.). Recruitment in Phase III will occur only in PBGs where it is feasible to return.

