### **Sample Selection via Convenience Sampling- Northeast Texas Region**

Study personnel from the Northeast Texas region will approach each PBG randomized to the study by mapping out all streets in the selected PBG using Google Maps. On each PBG map, they will identify community organizations where recruitment may be conducted with priority to those shown as salient in the social network analysis. In collaboration with selected organizations, study personnel will screen organization/event attendees by introducing themselves and the study, verifying eligibility, and scheduling an appointment at the individual's home where the remainder of the baseline visit may take place (unless the participant prefers to complete the entire baseline visit at that time). Staff will primarily recruit community members at these community events, but recruitment strategies may include posting recruitment fliers/posters at collaborating clinics, organizations, and businesses. Interested individuals will then call the contact listed on the poster to get more information about the study and learn how to participate. Study personnel can then screen the individual over the phone and if eligible, can schedule an appointment at the individual's home, where the remainder of the baseline visit will take place. Each community-based recruitment attempt, successful or unsuccessful, will be recorded on a tracking sheet as described in the previous paragraph.

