## Project Materials

### Intervention Arms:

**Multilevel Community Just-In-Time Network informed Adaptive Intervention (MC-NET-JITAI):** As previously described, recruitment of participants to the MC-NET-JITAI will take place at the participant's home or at one of the salient community organizations that our participants look to and interact with around COVID-19 topics identified through the social network data. CHWs will consent and enroll participants in the MC-NET-JITAI from the randomized PBGs. MC-NET-JITAI will include Community Health Workers (CHW) providing the participant with a batch of 4 rapid antigen tests that can be shared with people in the household or other close contacts if needed, a COVID-19 resource flier tailored to the study region and updated information about COVID-19 testing and vaccination. The intervention will consist of enhanced behavioral and educational text messages, up to three messages each week, providing updates on COVID-19 testing and vaccination. The text messages will include digitally-delivered intervention content such as a video with low-literacy instructions for administering the rapid antigen tests, guidance if they tested positive (e.g., quarantine, notify contacts, wearing a mask), and other relevant strategies and content focused on increasing COVID-19 testing and vaccination. The CHWs will also be available by phone to the participants for any follow-up questions. CHW will follow up via text, email and/or phone with the participants during the two months post-enrollment. In addition to the intervention, the participants will be asked to complete the pre and post-test surveys. Post surveys will be administered online, over the phone, or in person two months after the initial intervention.

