## Data Collection

The front-end web app will be accessible to external users on the UTHealth School of Public Health web domain at <https://redcap.uth.tmc.edu/>. Project staff will be provided login credentials specific to their role. For instance, the research coordinator for the survey will have full administrative control over the local application and datasets stored in the back-end server, including the ability to create new projects, modify project components, adjust the survey programming, and export survey results in various formats at any time. “Lead” users will be able to initiate surveys, open and close surveys for editing, and send reminders to participants automatically via phone or email. “Leads” will also be able to track the progress of other projects, and staff during “Interviewers” will be able to navigate the application to administer surveys and to track recruitment following the procedures described above.

The project coordinator responsible for REDCap will perform quality assurance and quality control checks on the database collected weekly to identify inconsistent data points, missing data, and incomplete data collection.

Two forms will be prepared for each region. One form will be to administer and collect the Phase III main study survey among enrolled intervention participants and will be initiated by project staff in person upon enrollment. We will also use REDCap to administer follow-up surveys two months after the participant completes their first survey, which will be done during a phone call or in person with a staff member who records the responses. After multiple attempts to complete the survey via phone or in person, we will reach out to the study participant with a secondary option to complete the follow-up survey via email or text message.

All surveys initiated in REDCap will have a unique survey identifier for the individual participant and the region where the survey is taking place and will be automatically anonymized. Phase III main study survey responses will also be iterated with proper data points identifying the census block group where the participant was recruited.

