## Statistics

**Statistical Analysis - Main Study Primary Outcomes.** We will conduct a series of analyses regarding the primary outcome variable - testing for COVID-19. First, we will conduct McNemar's test on data from the prospective cohort only. In addition to the test p-value, the odds ratio of COVID-19 testing for post-intervention versus baseline will be evaluated to assess the intervention effect. Second, based on both the prospective cohort and historical controls, we will find inferences for the ratio of odds ratios for intervention versus control. Third, using the prospective cohort, we will build a multi-level generalized linear mixed model (GLMM) including time as a fixed effect factor to evaluate intervention effect. Multiple random effects will be specified to account for the hierarchical structure of persons nested within PBGs nested within regions. Additionally, we will test variables such as individual demographics and baseline measures of rapid testing uses and include significant variables as the fixed effect factors. We will also test the PBG-level of Social Determinants of Health (SDOH) (e.g., % of minority, % of people with no insurance) to investigate the SDOHs as a potential effect modifier on the intervention effectiveness. We will also compute various network measures based on personal networks and organization affiliation patterns associated with COVID-19-related outcomes. Finally, we will build a GLMM to data of both the prospective cohort and historical controls. We will specify proper random effects to account for hierarchical nesting structure.

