### Sample Size for Testing the primary hypothesis in this study.

We have estimated the sample size of the prospective cohort based on the primary hypothesis that individuals experiencing the intervention of Phase III will have higher levels of effective use of SARS-CoV-2 testing than their testing at baseline. The McNemar test, together with the odds ratio (OR) of COVID-19 testing for post-intervention versus baseline, will be used to assess the intervention effect. Preliminary data yielded a discordance of 19% between baseline and follow-up measurements. The ORs were 3.4, 2.3, and 2.3 for Harris, Cameron, and NETX, respectively. The OR for the pooled data was 2.55. We use an OR of 2.5 and a discordance of 19%, which represents an 8% difference in the proportion of testing at follow-up compared to baseline, to size the prospective cohort. For a one-sided test at the significance level of 2.5%, a **sample size of 237 is needed to provide 80% power** for confirming the intervention effect. To allow for a **45% loss to follow-up**, 431 participants need to be enrolled at baseline. The table below provides the size options for a one-sided McNemar test of alpha 2.5% and power 80%.

Proportion of discordance	Odds ratio (OR)	Difference in proportion of testing pertaining to OR	Required sample size	Enrollment allows for a 35% loss to follow-up	Enrollment allows for a 45% loss to follow-up
0.19	2	6%	393	605	715
0.19	2.5	8%	237	365	431
0.19	3	9.5%	177	273	322
0.3	1.5	6%	681	1048	1239
0.3	1.727	8%	387	596	704
0.3	2	10%	249	384	453
0.3	2.75	14%	128	197	233

**Statistical Analysis - MC-NET-JITAI.** We will analyze the secondary outcome measures using the McNemar test, conditional logistic regression model, generalized linear mixed model (GLMM). The enrolled individuals completing the follow-up survey constitute the analysis set. In GLMM, we will specify proper random effects to account for hierarchical nesting structure. Secondary analyses will examine the relation between knowledge, attitudes, and intentions on testing and vaccination decisions and we will use the same multilevel GLMM models.

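### The confirmatory McNemar test and its 80% power assume independent pairs although recruitment is by block group; the effect is small unless change clusters by several percent

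*Combined protocol and SAP*

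**What the plan says.** The sample-size section of the combined protocol and SAP rests the primary hypothesis on a paired before-after comparison: "The McNemar test, together with the odds ratio (OR) of COVID-19 testing for post-intervention versus baseline, will be used to assess the intervention effect". It assumes 19% discordance and an odds ratio of 2.5, with a one-sided 2.5% level, and arrives at 237 completers for 80% power and 431 enrolled at 45% loss. It gives no intracluster correlation, design effect, number of PBGs or statement of independence.

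The Statistics section lists McNemar's test on the prospective cohort first. Nesting appears in the third analysis, a GLMM with time as a fixed effect: "Multiple random effects will be specified to account for the hierarchical structure of persons nested within PBGs nested within regions". The final GLMM, on both cohorts, also promises suitable random effects without naming them.

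Recruitment goes PBG by PBG. The number of PBGs in Phase III is not stated. General Information says of Phase II: "A sample of intervention PBGs were randomly selected from across the three study regions and assigned to one of two intervention study arms". Phase III reuses that sample, and Study Design narrows it again: "Recruitment in Phase III will occur only in PBGs where it is feasible to return". The Data Collection section says survey responses will carry "data points identifying the census block group where the participant was recruited".

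**The concern.** The test that is sized and used to confirm the effect ignores a nesting that the plan's own later models recognise. Stable differences between PBGs in testing level largely cancel within pairs, so they do little harm. What would matter is people in the same PBG tending to change together between baseline and follow-up.

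The documents offer some reasons why that correlation may not be zero. In Northeast Texas, when staff map a PBG, "they will identify community organizations where recruitment may be conducted with priority to those shown as salient in the social network analysis", and the other two regions also recruit partly through organizations. Each participant receives "4 rapid antigen tests that can be shared with people in the household or other close contacts if needed".

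If change does cluster, the McNemar error can exceed 2.5%, the odds-ratio interval is too narrow, and a test that holds its error has less than the stated power. Because the PBG number is missing, a reader cannot judge whether this is harmless.

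**Working it through.** **1. Reproduce 237.** Inputs from the sample-size section: discordance 0.19, OR 2.5, one-sided 0.025.
- Cell probabilities: 0.19 × 2.5/3.5 = 0.1357 and 0.19 × 1/3.5 = 0.0543. The difference is 0.0814, which the plan rounds to 8%.
- Exact test: the discordant count m follows Bin(n, 0.19). Given m, test p = 0.5 against true p = 2.5/3.5 = 0.714.
- Power is 0.7982 at n = 236 and 0.8001 at n = 237. The true size at 237 is 0.018.
- Enrolment: 237/0.55 = 431.
- In all seven rows of the plan's table, the stated n is the smallest that reaches 80% under this formula. The table therefore uses a design effect of 1.

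**2. Number of PBGs, K.** 120 randomized less 40 control gives at most 80 intervention PBGs. Phase II sampled these and Phase III keeps the feasible ones, so 80 is a ceiling. I take K = 80, 60 and 40 as assumptions. Mean completers per PBG are 237/80 = 3.0, 237/60 = 4.0 and 237/40 = 5.9.

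**3. What the documents suggest about the ICC.** The only heterogeneity data are regional: "The ORs were 3.4, 2.3, and 2.3 for Harris, Cameron, and NETX, respectively". If discordance is 19% in each region, the difference is 0.19 × (OR − 1)/(OR + 1) = 0.1036, 0.0748 and 0.0748.
- With 2:1:1 weights the mean is 0.0892 and the between-region variance is 0.000207.
- The total variance of change is 0.19 − 0.0892² = 0.182.
- The ratio is about 0.001. This is a region-level value and does not bound the PBG-level ICC.

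**4. Effect of clustering.** The ICC of change is assumed at 0.01, 0.02 and 0.05.
- Design effect with equal sizes: DEFF = 1 + (237/K − 1) × ICC. For K = 40 and ICC 0.05 it is 1 + 4.925 × 0.05 = 1.246.
- Approximate error of the unadjusted asymptotic test: P(Z > 1.96/√DEFF). For that case it is P(Z > 1.756) = 4.0%.
- Exact-test error and PBG-robust power come from simulation: Dirichlet-multinomial outcomes (gain, loss, no change) within PBG, 237 completers. The robust test is mean change with cluster variance × K/(K − 1) and t on K − 1 df.

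| K | ICC | DEFF | Asymptotic error, by formula | Exact error, simulated | Robust power, simulated |
|---|---|---|---|---|---|
| 80 | 0.01 | 1.020 | 2.6% | 1.9% | 82% |
| 80 | 0.02 | 1.039 | 2.7% | 2.0% | 82% |
| 80 | 0.05 | 1.098 | 3.1% | 2.2% | 79% |
| 60 | 0.01 | 1.030 | 2.7% | 1.9% | 82% |
| 60 | 0.02 | 1.059 | 2.8% | 2.1% | 80% |
| 60 | 0.05 | 1.147 | 3.4% | 2.5% | 77% |
| 40 | 0.01 | 1.049 | 2.8% | 2.0% | 80% |
| 40 | 0.02 | 1.099 | 3.1% | 2.3% | 78% |
| 40 | 0.05 | 1.246 | 4.0% | 3.0% | 73% |

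Simulated asymptotic error at ICC 0.05 is about 3.1%, 3.3% and 3.8% for 80, 60 and 40 PBGs. At ICC 0.02 it is at most about 3.3%. Separate runs differ by up to about 0.3 points in error and 1 point in power. The robust test's own error is 2.4-2.6% in every equal-size case.

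**5. Uneven PBG sizes** (assumed CV 0.6, ICC 0.05). Exact McNemar error is 2.7%, 3.1% and 3.8% for 80, 60 and 40 PBGs. Power with a jackknife-type robust variance is 76%, 73% and 68%.

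**6. Cost if nothing clusters.** Asymptotic McNemar at 237 has power 83.6% and size 2.5%. The robust test has 83.0%, 82.6% and 81.7% for 80, 60 and 40 PBGs, a loss of 0.6, 1.0 and 1.9 points.

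**The case against.** The strongest reply is that both drivers are assumed. The documents report no PBG-level ICC, and the regional odds ratios give no support for a large one. Enrolment is one person per household, and text messages go to individuals. Sharing kits with close contacts correlates participants' changes only if those contacts also enrol, which the documents do not say. All of this stands. It is why the point is conditional and why no increase in enrolment is asked for.

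A second reply is that the later GLMMs already deal with nesting. This holds in part. Multiple random effects could include one for PBG-level change, but they are not specified: a PBG intercept alone would cover level, not change. Those models are also not the sized test, and nothing says which result prevails if they disagree with McNemar.

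Third, the planned test's own power barely falls: simulated exact McNemar power at ICC 0.05 is 78.6%, 78.4% and 77.1% for 80, 60 and 40 PBGs. This is correct. The lower robust figures are the power of a test that holds its error. A cruder calculation, which puts 237/DEFF into the exact formula, gives 75.6%, 73.5% and 69.0%. It is lower because it keeps the exact test's conservative 1.8% size.

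A reader might infer that 40 or fewer PBGs with any clustering is enough for material harm, or that a robust test costs nothing. Neither is supported. At 40 PBGs and ICC 0.01-0.02, exact error stays below 2.5% and robust power is 78-80%. The robust test looks free only beside the conservative exact test; against the asymptotic test it costs up to about 2 points. An exact ICC at which error crosses 2.5% would also be false precision, because the plan does not say which McNemar version it will use.

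**Conclusion.** The point holds in a limited form. The confirmatory McNemar test and its 80% power at 237 rest on an unstated assumption of independent pairs, and the nesting is modelled only in analyses that were not sized.

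The size depends on two quantities that the documents do not give. With 40 to 80 equal-sized PBGs and an ICC of change up to about 0.02, the effect is small. It becomes noticeable at an ICC near 0.05: exact / asymptotic error is about 2.3 / 3.1% with 80 PBGs, 2.5 / 3.3% with 60 and 3.0 / 3.8% with 40, and robust power is about 79%, 78% and 73%. Uneven PBG sizes make it worse.

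The documents do not show that the confirmatory test is invalid or the study underpowered. They leave both open, and closing the gap is a cheap improvement.

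**What to change.** - Base the confirmatory paired test and its odds-ratio interval on a PBG-clustered variance. Options are a cluster-adjusted McNemar test, or GEE or mean change with PBG-robust variance and a small-sample correction; a jackknife-type correction suits uneven PBG sizes.
- Use PBG-clustered variance for the ratio of odds ratios as well.
- State the number of Phase III PBGs.
- State that 80% power assumes no within-PBG correlation of change, or show power over a range of ICC at the actual PBG number. Enrolment stays at 431.

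The cost is SAP wording and standard software, since PBG is already recorded. If nothing clusters, about 0.5-2 power points are lost against asymptotic McNemar with 40-80 PBGs. If change does cluster, intervals are somewhat wider.

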## **Background Information**

Vulnerable populations in the U.S. experience significant COVID-19 disparities, and individuals with medical comorbidities have suffered disproportionately. Additionally, Hispanics are 1.5x more likely to be infected, 2.3x more likely to be hospitalized, and 1.8x more likely to die from COVID-19 compared to White, Non-Hispanics. Blacks are 2.4x more likely to be hospitalized, and 1.7x more likely to die. The Phase III main study builds on our RADx-UP Phase I and Phase II work reaching these populations in three racially diverse regions: Houston/Harris County, South Texas, and Northeast Texas, leveraging the partnerships and resources of the Center for Clinical and Translational Science (CCTS) to increase SARS-CoV-2 testing, vaccination, and mitigation behaviors to reduce COVID-19 among underserved populations in Texas. The pandemic landscape and people's experiences with testing, infection, and vaccination have changed dramatically over the past two years. Vaccines have become available, testing access in local communities has waxed and waned, and attitudes toward COVID-19 severity and susceptibility have changed.

Antigen self-testing kits are more available at this stage in the evolution of COVID-19, but among vulnerable populations, use is still low, and instructions for antigen testing are not typically designed for low health literacy populations. Navigating the shifting testing-decision landscape is confusing to the public (test availability for free versus charged or requiring insurance; testing and vaccination locations change; PCR versus antigen testing; home tests versus clinically delivered; symptom-based testing, exposure-driven testing, serial testing, resources to trust or not trust, etc.). Studies are needed to explore access and use of antigen tests, including serial testing among vulnerable populations, and studies are needed to examine if low health literacy designed interventions improve COVID-19 testing decisions and completion behaviors.

The proposed study will focus on understanding factors associated with *rapid* SARS-CoV-2 testing, specifically.

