## Study Design:

**RADx-UP Phases I & II.** (The parent studies) We conducted a three-arm group randomized trial to assess the impact of multilevel interventions influencing motivation and access to testing: Arm 1) Community Engaged Just-In-Time Adaptive Intervention (Community JITAI) where we met regularly with community partners and exchanged community-specific information about COVID-19 (testing, infection rates, etc), Arm 2) Standard multilevel intervention (MLI), and a usual practice condition. We randomized 120 PBGs identified as communities with high levels of disparities across our three geographic regions to each condition using a covariate adaptive Randomization (Minimization) Schedule.

The primary outcome for the Phase I and II studies was community-level SARS-CoV-2 testing (primarily PCR testing). This measure was assessed bi-monthly throughout the study. We also conducted an embedded panel study to 1) compare the effectiveness of the CHW-Facilitated Self-Sampling Intervention (FSSI) vs. CHW Testing Navigation Intervention (TNI). In the ongoing study, we also collected social network data on a sub-sample of individuals to explore the influence of social networks on testing decision-making and behavior.

**RADx-UP Phase III:** Our Phase III study design focuses on **vulnerable communities** selected to intervention and control conditions and takes advantage of the fact that these communities were randomized to conditions using methods to ensure balanced arms. In Phase III, we will combine the two intervention conditions (TNI & FSSI), and will receive the MC-NET-JITAI. The study will include PBGs from each of the two intervention conditions in Phase II; they will be matched to the comparison PBGs on variables such as size, vaccination and testing rates, and the disparities index with the control group. The intervention will last 8 weeks; individuals will be recruited and asked to complete a survey (including RADx-UP common data elements).

In Phase III, we will utilize a historical control group consisting of 400 participants from the control arm who completed the baseline and follow-up surveys in the Phase II embedded study.

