### Control Arm:

**Control PBGs:** Since we are utilizing a historical control study design, we are not recruiting any new control participants for this Phase III main study. Instead, we will analyze the survey data already collected from the Phase II embedded study control participants.

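### The test of SDOH as an effect modifier sits in the cohort-only model, where a background testing trend that differs by SDOH cannot be told apart from an intervention effect that differs by SDOH

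*Combined protocol and SAP*

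**What the plan says.** The Statistics section (main study primary outcomes) lists the analyses in order. McNemar's test in the cohort comes first, and a ratio of odds ratios against historical controls second. The third is described as "using the prospective cohort, we will build a multi-level generalized linear mixed model (GLMM) including time as a fixed effect factor", the time factor being there to evaluate the intervention effect. Covariate selection and the SDOH test follow. The examples given are the percentage of minority residents and of uninsured residents, and the stated aim is "to investigate the SDOHs as a potential effect modifier on the intervention effectiveness". Only then comes the last model: "Finally, we will build a GLMM to data of both the prospective cohort and historical controls". For that model the text mentions random effects for nesting and lists no fixed effects.

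Three other places bear on the point:
- Objectives defines effectiveness as a comparison with a historical control group.
- Control Arm confirms that the controls are not concurrent: "we will analyze the survey data already collected from the Phase II embedded study control participants". Study Design puts their number at 400.
- Background Information says that "testing access in local communities has waxed and waned, and attitudes toward COVID-19 severity and susceptibility have changed".

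**The concern.** In the cohort-only model everyone receives the intervention, so the only available modifier term is SDOH × time. It measures whether testing changed by different amounts across block groups, for whatever reason. Calling that modification of effectiveness attributes the whole difference to the intervention.

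Some features of the plan could produce change unrelated to the intervention. Testing access shifted over time. Study Population excludes anyone tested in the 30 days before enrolment, which can create a rise from baseline. Under Recruitment, follow-up may fall anywhere from 5 weeks to the end of data collection in that block group, roughly 4 months. The documents do not say that any of these varies with SDOH, but nothing in the cohort-only model would show it if they did.

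The programme exists to address testing disparities. A statement that the intervention works better or worse in more disadvantaged block groups would therefore carry weight with readers.

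**Working it through.** **1. The plan's own figures.** Inputs from the sample-size section: discordance 0.19, OR 2.5, one-sided alpha 2.5%, power 80%, 45% loss.
- Difference in proportions: 0.19 × (2.5 − 1)/(2.5 + 1) = 0.081, stated as 8%.
- An exact McNemar test at N = 237 has power 0.800.
- Enrolment: 237/0.55 = 430.9, so 431.

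These reproduce and are not in dispute.

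**2. What the term estimates.** Let T(s) be the background log-OR for time and E(s) the intervention's log-OR at SDOH level s. In one group,

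SDOH × time = [T(1) − T(0)] + [E(1) − E(0)].

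Only the sum is estimable. A constant effect OR of 2.5 with background ORs of 1.0 and 1.5 gives pre-post ORs of 2.5 and 3.75. No background trend with effects of 2.5 and 3.75 gives the same two numbers.

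**3. Illustration.** Assumptions: two equal SDOH halves, intervention OR 2.5 in both, 19% discordance in both, no clustering, and a drift factor f in one half only. The drift factors are not in the documents.
- Discordant pairs per half: 237 × 0.19/2 = 22.5.
- Variance of a log-OR from m discordant pairs: 1/b + 1/c, with b = m × OR/(1 + OR) and c = m − b.
- Reference half, OR 2.5: b = 16.08, c = 6.43, variance 0.2176.

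| f | OR in drifting half | Variance | SE of difference | log f / SE | Rejection, two-sided 5% |
|---|---|---|---|---|---|
| 1.5 | 3.75 | 0.2672 | 0.696 | 0.582 | 0.084 + 0.006 = 9.0% |
| 2.0 | 5.0 | 0.3198 | 0.733 | 0.946 | 0.155 + 0.002 = 15.7% |

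The estimated ratio of ORs targets f, although the true modification is 1.0.

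**4. Sensitivity to method and sample size.** With so few discordant pairs the Wald approximation runs high. A simulation of 20,000 trials under the same assumptions, adding 0.5 to each cell, gives:

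| Analysed | No drift | f = 1.5 | f = 2.0 |
|---|---|---|---|
| 237 | 3.3% | 6.0% | 10.5% |
| 431 | 4.1% | 10.5% | 21.9% |

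The false-positive rate rises with N because the bias stays while the standard error shrinks.

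**5. What the three-way term does.** Subtracting the same contrast in the controls gives

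[E(1) − E(0)] + [T(1) − T(0)] in Phase III − [T(1) − T(0)] in Phase II.

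The trend cancels only if the two phases share it. When 400 simulated controls are given the same drift, the ratio returns to about 1.0 (0.995 at f = 1.5, 0.979 at f = 2.0) and rejection is 3.7% and 3.3%. That result follows from the shared-drift assumption.

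**6. Its precision.** Assume 400 controls with 19% discordance, OR 1 and an even split. There are 38 pairs per half, variance 2/19 = 0.1053 in each.
- SE, cohort only: √(2 × 0.2176) = 0.66.
- SE, three-way: √(0.4353 + 0.2105) = 0.80.
- Ratio of ORs detectable with 80% power at two-sided 5%, exp[(1.960 + 0.842) × SE]: about 6.3 cohort-only and 9.5 three-way.

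**The case against.** The strongest reply is that placement is inferred from word order. The SDOH sentence names no data set, and the combined model's fixed effects are left open, so SDOH may have been meant for it too. That much stands: a reader might infer that the plan rules SDOH out of the controlled comparison, and it does not. But the sequence puts the test inside the cohort-only step, and nothing says that it carries over. Even on the generous reading, the model and the term need naming.

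Two other inferences go too far. One is that the control data would settle the question. They were collected in Phase II, and Background Information itself describes changing conditions, so equal trends across phases cannot be taken for granted. The other is that Background Information shows access changing differently by SDOH. It reports change over time only.

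It is also fair to say that the wording on a potential modifier is exploratory, and that Study Design has intervention block groups matched to comparison ones on testing rates and a disparities index. Matching helps a comparison with controls; it does nothing for an interaction estimated without them. Finally, the proposed term has little power, as step 6 shows. That is a reason to label it exploratory, but not a reason to interpret the confounded term as modification.

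**Conclusion.** The point holds as one of identification. Followed in the order written, the plan would give the name of effect modification to a quantity that mixes trend and effect, although Objectives defines effectiveness against controls. The bias equals the full drift factor at any sample size. The inflation in false positives is modest at the planned size: about 9% and 16% by Wald for factors of 1.5 and 2.0, and 6% and 10.5% by simulation. These figures rest on assumed drift, an even split, 19% discordance, OR 2.5 in both halves and no clustering within block groups. The documents do not show that a differential trend exists, so it should not be concluded that the SDOH result will be wrong, only that the cohort-only model could not reveal it. The matter concerns a subsidiary analysis. The McNemar test and the figures of 237 and 431 are unaffected.

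**What to change.** - In the combined mixed model, specify SDOH as group × time × SDOH, attach the same census block-group measures to the control block groups, and label the analysis exploratory.
- In the cohort-only model, report SDOH × time as variation in pre-post change by SDOH, not as modification of intervention effectiveness.
- State beside the three-way result that it removes a differential trend only if the Phase II trend by SDOH matches that of Phase III, and that it is therefore a partial remedy.

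The cost is SAP wording and one data link. Data Cleaning already plans the use of block-group census data, and the combined model's nesting structure presumes that control records can be tied to their block groups. The price is precision: an SE of about 0.80 against 0.66 on the log scale, under the assumptions in step 6. The relabelling depends on no assumption about the controls and is worth making even if the three-way term is judged too imprecise to report.
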